## **Participant Selection**

Adult patients with confirmed MGD in a single practice limited to dry eye meeting the following criteria.

### Inclusion Criteria:

1. Subject can be of any gender or race
2. Subject must be 18 years of age or older at the time of informed consent
2. Subject must be able to understand and must sign an Informed Consent that has been approved by an IRB
3. Subject must have confirmed diagnosis of Meibomian Gland Dysfunction
4. Subject must agree to not wear contact lenses the day of the Study visit

### Exclusion Criteria:

1. History of intraocular or oculoplastic surgery within 6 months of Screening visit
2. History of ocular injury or trauma, chemical burns, or limbal stem cell deficiency within 3 months of the Screening visit
3. Active ocular infection or active ocular inflammation (including allergic conjunctivitis, vernal or giant papillary conjunctivitis) at time of Screening visit
4. History of ocular surface abnormality that may compromise corneal integrity
5. History of treatment with LipiFlow or iLux in either eye in the last 6 months
6. Allergy to topical proparacaine eye drops

### Total Number of Participants to be Enrolled:

The clinical site will enroll up to 42 subjects to ensure that 38 subjects have evaluable data for both treatments. With 38 evaluable subjects, this study will have 80% power to detect a half point difference between treatments on the 5-point Likert-style questionnaire, assuming within patient standard deviation of 0.75 points and at a significance level of 0.05.

## **Study Design / Methods / Procedures**

This study is an open-label, single site, crossover trial comparing LipiFlow Thermal Pulsation System to the iLux System based on patient acceptance, comfort, and preference. The proposed sample size is 42 subjects allowing for 10% dropout during patient screening.

2 Visits: Screening visit and Study visit

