### Screening visit (approx. 30 min)

1. Obtain Informed Consent
2. Obtain Patient demographics
3. Verify Inclusion and Exclusion criteria
4. Schedule for Study visit
5. Randomize in a 1:1 ratio to receive bilateral treatment initially with either LipiFlow or iLux

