### Randomization:

An envelope with 42 identical slips of paper with 21 labeled LipiFlow and 21 labeled iLux will be prepared prior to initiating the study for a 1:1 randomization ratio. After a subject has been

determined to meet entrance criteria and has signed the ICF, each subject will draw one slip of paper which will determine whether they receive either Lipiflow first or iLux first.

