#### Criteria for subject withdrawal by investigator

Subjects may be withdrawn from study treatment at any time if, in the opinion of the Investigator, continued treatment poses a risk to the subject.

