#### Statistical Analysis Plan

Descriptive statistics will be provided to summarize each treatment questionnaire response: N, mean, standard deviation, minimum, maximum, and median. Categorical or binary endpoints will be summarized by count and percentage. Other statistical tests of correlation, variance, or regression to be recommended by statistician and methods used will be reported in the final report.

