### Informed Consent (*Sterling IRB- Informed Consent Document Preparation service requested*)

Patients must have the study explained to them by a member of the study team, they must be provided enough time to consider their participation in the study and provided an opportunity to ask questions of the study team. Subjects must sign the most current version of an informed consent form (ICF) written and approved by an Institutional Review Board (IRB). All patients who sign an ICF are considered enrolled subjects in the study and will not undergo any study-specific assessments until after they have signed the ICF. Subjects may withdraw their consent to participate in the study at any time, for any reason. The study investigator may also withdraw subjects from the study at their discretion in order to protect the rights, safety, or welfare of the subject. All withdrawn subjects will be included in study analyses, but they will not be replaced. No missing data will be imputed.

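### Does the plan count 42 subjects at two different points, and so fall short of the 38 evaluable subjects its power needs?

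*Combined protocol and SAP*

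**What the plan says.** Five places in the combined protocol and SAP bear on the count.

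- *Total Number of Participants to be Enrolled* sets the cap and the target: "The clinical site will enroll up to 42 subjects to ensure that 38 subjects have evaluable data for both treatments". The same section claims 80% power with 38 evaluable subjects for a difference of 0.5 points, with a within-patient SD of 0.75 and a significance level of 0.05.
- *Study Design / Methods / Procedures*: "The proposed sample size is 42 subjects allowing for 10% dropout during patient screening".
- *Screening visit*: consent is step 1, "Verify Inclusion and Exclusion criteria" is step 3, and randomisation is step 5.
- *Randomization*: "An envelope with 42 identical slips of paper with 21 labeled LipiFlow and 21 labeled iLux" is prepared before the study starts. Once a subject has been "determined to meet entrance criteria and has signed the ICF, each subject will draw one slip of paper".
- *Informed Consent*: "All patients who sign an ICF are considered enrolled subjects in the study". Withdrawn subjects are not replaced, and missing data are not imputed.

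Loss after randomisation is possible. Subjects may withdraw consent at any time, and under *Criteria for subject withdrawal by investigator*, "Subjects may be withdrawn from study treatment at any time if, in the opinion of the Investigator", continuing poses a risk. On the analysis, the *Statistical Analysis Plan* section specifies descriptive summaries and leaves the rest open: "Other statistical tests of correlation, variance, or regression to be recommended by statistician".

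**The concern.** Read together, the enrolment cap and the definition of an enrolled subject make 42 a limit on signed consents. Consent comes before the eligibility check, so a screen failure uses one of the 42 places. The 10% allowance is attached to screening. On that reading the whole margin is used before anyone is treated, and about 38 subjects go forward.

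A subject who then withdraws between the two devices is neither replaced nor imputed, and so cannot count among the 38 with data for both. The envelope seems to point the other way: 42 slips, drawn only by eligible subjects, look like a plan to randomise 42. Both cannot be expected at once, because randomising 42 after a 10% screening loss takes about 42 / 0.90 = 46.7, so 47, consents, which is above the cap.

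At stake would be the stated power, since 38 is the smallest number that reaches 80% under a t-test. The 21:21 sequence split is also affected, as it is certain only if every slip is drawn.

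**Working it through.** **Inputs.** From *Total Number of Participants to be Enrolled*: difference 0.5, within-patient SD 0.75, alpha 0.05, 38 evaluable, cap 42. From *Study Design / Methods / Procedures*: 10% loss. From *Randomization*: 21 + 21 slips. Assumed, because the plan does not state them: a two-sided test, and a crossover t-test with n − 2 degrees of freedom.

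**1. Reproduce 38.** The SD of a within-subject difference is 0.75 × √2 = 1.061. The noncentrality at n = 38 is 0.5 / (1.061 / √38) = 2.906. With 36 degrees of freedom the power is 80.7%; at n = 37 it is 79.6%. So 38 is the smallest n reaching 80% under this test. The normal approximation gives n = (1.061 × (1.960 + 0.842) / 0.5)² = 35.3, so 36; the threshold depends on the test.

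**2. Reproduce 42.** 38 × 1.10 = 41.8, so 42. Dividing instead, 38 / 0.90 = 42.2, so 43. The plan's figure is within one subject either way.

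**3. Consent-cap reading, plan's own loss only.** Let the number evaluable be Binomial(42, 0.90).

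- Mean: 42 × 0.90 = 37.8.
- P(at least 38 evaluable) = 0.59.
- Power averaged over this distribution = 80.4%.

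**4. Randomised reading.** With all 42 randomised and evaluable, power is 84.6%. With 10% lost after randomisation, the distribution is that of step 3, and the average is again 80.4%.

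**5. Added loss after screening (assumed; the documents give no rate).**

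| Further loss | Proportion retained | Mean evaluable | P(at least 38) | Average power |
|---|---|---|---|---|
| 0% | 0.90 | 37.8 | 0.59 | 80.4% |
| 5% | 0.90 × 0.95 = 0.855 | 35.9 | 0.25 | 78.2% |
| 10% | 0.90 × 0.90 = 0.81 | 34.0 | 0.08 | 75.8% |

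At fixed numbers, power is 78.5% with 36 evaluable and 76.0% with 34. The difference detectable with 80% power moves from 0.495 points at 38 to 0.510 at 36 and 0.526 at 34.

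**6. Scale.** With all 38 evaluable and an SD of 0.77 instead of 0.75, power is 78.6%. An error of 0.02 in the assumed SD therefore costs 80.7 − 78.6 = 2.1 points, against 80.7 − 79.6 = 1.1 points for losing one subject.

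**7. Undrawn slips.** If 38 of the 42 slips are drawn, the split is 19:19 with probability 0.39 and can run from 17:21 to 21:17. Power is 80.7% at 19:19 and 80.3% at the worst split, a difference of 0.4 points.

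**The case for a change.** The strongest case for acting is operational. The site has to know whether to stop at 42 signatures or at 42 slips, and two people following the text could stop at different points. The claim that 42 will ensure 38 is a factual one, yet on the consent-cap reading it is met with probability of only 0.59, even with no loss beyond the plan's own 10%. Later loss is plainly foreseen: withdrawal is allowed at any time, and a slit-lamp check precedes each treatment. None of it is budgeted, replaced or imputed. Clarifying the wording would cost nothing.

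Part of this stands. The verb is too strong for a capped design without replacement; 38 is close to the expected number, not an assured one. No margin for loss after screening is stated.

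The contradiction with the envelope does not stand. The *Randomization* section never says that 42 will be randomised. With enrolment of up to 42, an envelope of 42 slips is what is needed to cover the maximum, and slips left over contradict nothing. All the passages can then be read as one consent cap.

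Nor would the available remedies earn their place. Softer wording on the same 42 consents leaves the expected 37.8 and the 0.59 where they are. Raising consents to 47 would mean, at 10% screen failure, treating about four more people with both devices (42 − 37.8 = 4.2), although no figure stated in the plan is missed.

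**Conclusion.** The concern does not call for a change. Neither 38 nor 42 is miscalculated. On the less favourable reading, and using only the plan's own 10%, average power is 80.4%, so the stated 80% holds. Reading 42 as the number randomised can only match or improve on that when loss after randomisation is 10% or less. An uneven sequence split costs at most 0.4 points with 38 slips drawn.

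What remains is loose wording about where subjects are counted. A trial team would settle it in practice by treating 42 as the ceiling and reporting the numbers consented, randomised and evaluable. A site following the text at either counting point would still reach sound results.

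This rests on a two-sided crossover t-test, which the plan does not name, and on little loss after screening. Both treatments are given at a single visit, which limits the opportunity for dropout between them. If a further 5% to 10% were lost, average power would be about 78% to 76%, a modest shortfall resting on a rate the documents do not supply.

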### Screening visit (approx. 30 min)

1. Obtain Informed Consent
2. Obtain Patient demographics
3. Verify Inclusion and Exclusion criteria
4. Schedule for Study visit
5. Randomize in a 1:1 ratio to receive bilateral treatment initially with either LipiFlow or iLux

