### Study visit (approx. 100 min)

1. Perform slit lamp evaluation to verify no abnormal clinical findings prior to treatment
2. Perform either bilateral Lipiflow or bilateral iLux per Screening visit randomization
3. Patient fills out 5 Point Likert Scale questionnaire about treatment received
4. Perform slit lamp evaluation to verify no abnormal clinical findings prior to treatment
5. Perform the other bilateral Lipiflow or bilateral iLux procedure  $\geq$  1-hour after first
6. Patient fills out 5 Point Likert Scale questionnaire about treatment received
7. Patient answers final Patient Preference Question

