### Treatments

Both procedures will be performed on both eyes on the same day at least one (1) hour apart.

1. Eye makeup shall be removed.
2. The device shall be prepared for use in accordance with the Instructions per User Manual for the device to which the subject is randomized.
3. Proparacaine eye drops will be instilled in both eyes.
4. Therapy will be delivered in accordance with the User Manual for the device to which the subject is randomized.
5. Throughout the treatment visit, subjects will be assessed for any adverse events.

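### Minor, cheap improvement: draw the treatment order at the Study visit, after the first slit-lamp check, so that no-shows and pre-treatment holds cannot depend on it

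*Combined protocol and SAP*

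**What the plan says.** - **Timing of the draw.** Under *Screening visit*, the fifth and last step, after eligibility is verified and the Study visit is scheduled, is "Randomize in a 1:1 ratio to receive bilateral treatment initially with either LipiFlow or iLux".
- **Method.** Under *Randomization*, "An envelope with 42 identical slips of paper with 21 labeled LipiFlow and 21 labeled iLux will be prepared prior to initiating the study", and "each subject will draw one slip of paper which will determine whether they receive either Lipiflow first or iLux first". This section makes the draw depend only on eligibility and signed consent. It names no visit.
- **What follows.** Under *Study visit*, step 1 is "Perform slit lamp evaluation to verify no abnormal clinical findings prior to treatment". Step 2 is "Perform either bilateral Lipiflow or bilateral iLux per Screening visit randomization".
- **Masking.** *Study Design / Methods / Procedures* describes an open-label crossover. No section hides the order after the draw or masks the slit-lamp examiner to it.
- **Dropout.** The same section sets 42 subjects to allow for 10% dropout and places that dropout in patient screening. *Total Number of Participants to be Enrolled* needs 38 evaluable.
- **Who counts.** Under *Informed Consent*, "All patients who sign an ICF are considered enrolled subjects in the study" and "All withdrawn subjects will be included in study analyses, but they will not be replaced". Missing data are not imputed.
- **Analysis.** *Statistical Analysis Plan* gives descriptive summaries and leaves other tests to the statistician. It specifies no period adjustment.

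The documents do not give the interval between the visits, the number expected to be lost after the draw, or what follows an abnormal slit-lamp finding.

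**The concern.** Between the draw and the first treatment there are two points at which a subject can drop out: not returning, and being held at the slit-lamp check. At both, the subject has seen the slip and staff can know the order. If that knowledge influenced who is lost, the two order groups would no longer be comparable as randomised.

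This could reach the device comparison in two ways:

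- The subjects lost because of the order also differ from those retained in their LipiFlow-minus-iLux difference.
- The analysis has no period term, and the resulting imbalance in order carries part of a period effect into the raw difference.

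If the order does not exist until just before treatment, neither a no-show nor a hold at the first check can have been influenced by it.

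**Working it through.** **Inputs from the plan.** 42 slips, 21 per order; 38 evaluable; target difference 0.5 point; within-patient SD 0.75; significance level 0.05; dropout 10%.

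**Assumptions of this review.** Two-sided test. D, the gap in LipiFlow-minus-iLux difference between lost and retained subjects of one order, is taken as 0.5 to 1.0 point. A period effect of 0.5 point is used for illustration. The documents give no value for either.

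**1. The plan's own figure.** With 0.75 as the SD of a single measurement within a patient, the SD of the paired difference is 0.75 × √2 = 1.061. A paired t-test with n = 38 then has 80.8% power (37 df) or 80.7% (36 df), and 38 is the smallest n that reaches 80%. The stated power reproduces. For dropout, 42 × 0.9 = 37.8, so the allowance is about 4 subjects. Moving the draw changes none of this.

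**2. Shift per order-caused loss, period-adjusted.** Let d = LipiFlow minus iLux. The estimate is (mean d in order A + mean d in order B)/2. Losing k of 21 in one order moves that order's mean by kD/21, and so moves the estimate by kD/42. For k = 1:

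- D = 0: zero
- D = 0.5: 0.5/42 = 0.012 point
- D = 1.0: 1.0/42 = 0.024 point

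The standard error is (1.061/2) × √(1/21 + 1/17) = 0.173 at a 21:17 split. One such loss is therefore 0.012/0.173 = 0.07 to 0.024/0.173 = 0.14 of a standard error.

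**3. Raw difference without a period term.** With k losses in one order, the imbalance passes k/(42 − k) of any period effect into the raw difference. For k = 1 this is 1/41 = 2.4%, or 0.012 point for a period effect of 0.5.

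**4. What moving the draw cannot remove.** Take four equally atypical subjects.

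- Lost 4:0, they shift the estimate by 4D/42.
- Lost 2:2, each order's mean moves by 2D/21, and the average is again 4D/42.
- Lost before any draw, the mean of the retained 38 differs from the mean of all 42 by 4D/42.

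Only losses caused by knowing the order are removable.

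**5. Balance if only 38 slips are drawn** (hypergeometric, 38 of 42 with 21 of each kind):

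| Split | Probability |
|---|---|
| 19:19 | 39.4% |
| 20:18, either way | 49.9% |
| 21:17, either way | 10.7% |

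The evaluable split has the same distribution if all 42 draw at Screening and 4 are then lost for reasons unrelated to order. Power for the period-adjusted contrast is 80.7% at 19:19 and 80.3% at 21:17.

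**The case against.** The case for leaving the plan alone is substantial. The screening and study-visit steps agree with each other, so there is no contradiction to repair. The order decides only which device comes first, because *Treatments* gives both devices to every subject on the same day. *Costs to Participants* offers the treatments free in return for taking part, so a subject who stays away gives up both. The Study visit is booked before the draw, so the order cannot affect the appointment made at Screening. The plan's dropout is placed in screening, and eligibility is checked before the draw, so some or all of the four allowed losses may come before any order exists. All of this stands and makes the benefit small. It does not remove the benefit, because a subject can still fail to return, or be held, with the order known.

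Three stronger readings are tempting, and the documents do not support them.

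- **That the device comparison is biased.** Nothing shows that knowing the order causes losses, or that those lost would differ in their device difference.
- **That the bias could reach 10% to 19% of the target.** That is 4D/42 = 0.048 to 0.095 point for D of 0.5 to 1.0. It needs all four losses to fall after the draw, all to be caused by the order, all to be in one order, and all to be atypical by an assumed D that is one to two times the whole target. Step 4 of the check shows that the same figure arises from losses that the later draw cannot prevent.
- **That the envelope must be replaced by a sequence of numbered sealed envelopes.** That is a separate matter of concealment. The timing point does not need it.

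**Conclusion.** The sequence is as described, and the exposure is avoidable. It is a minor point and not an error in the plan. The effect is zero unless knowing the order causes losses. Otherwise it is about 0.012 to 0.024 point per order-caused loss in a period-adjusted estimate, for an assumed D of 0.5 to 1.0, and proportionally less for a smaller D. These figures take 21 subjects per order at the draw and 0.75 as the per-measurement SD. The second assumption affects only the comparison with the standard error.

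The later draw should not be presented as preserving an exact 21:21 randomised split. The slips stay 21 and 21, but subjects lost before the draw leave slips undrawn. Nor does it reach losses between the two treatments, including at the second slit-lamp check, where the device just received could matter.

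**What to change.** - ***Screening visit*:** delete step 5.
- ***Study visit*:** directly after step 1 insert: *A subject who goes on to treatment draws one slip; record subject number, order, date and time.* In step 2, refer to the Study visit randomisation instead of the Screening one.
- ***Randomization*:** add that the draw takes place at the Study visit, after the first slit-lamp evaluation. The envelope of 42 slips can stay.
- ***Informed Consent*:** in place of the clause including all withdrawn subjects in the analyses, write: *Subjects lost before the draw are counted in the subject flow, have no assigned order and are not part of the device comparison. Subjects withdrawn after the draw are included in study analyses and reported by assigned order.* The rule against replacement is unchanged.

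The inserted step depends on who goes on to treatment, which the documents leave undefined when the slit-lamp finding is abnormal. That is for the sponsor to settle, and no rule is proposed here.

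**Cost.** Wording in four sections and one record per draw, with no extra subject, visit or staff. There are two downsides. First, the first device cannot be set up before the draw. However, *Treatments* lists as its second step "The device shall be prepared for use in accordance with the Instructions per User Manual for the device to which the subject is randomized", so a draw after the slit-lamp check can still come before it, and both devices are needed at every Study visit anyway. Second, if fewer than 42 slips are drawn, the randomised split may be unequal, as the check shows for 38.

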### Study visit (approx. 100 min)

1. Perform slit lamp evaluation to verify no abnormal clinical findings prior to treatment
2. Perform either bilateral Lipiflow or bilateral iLux per Screening visit randomization
3. Patient fills out 5 Point Likert Scale questionnaire about treatment received
4. Perform slit lamp evaluation to verify no abnormal clinical findings prior to treatment
5. Perform the other bilateral Lipiflow or bilateral iLux procedure  $\geq$  1-hour after first
6. Patient fills out 5 Point Likert Scale questionnaire about treatment received
7. Patient answers final Patient Preference Question

### Treatments

Both procedures will be performed on both eyes on the same day at least one (1) hour apart.

1. Eye makeup shall be removed.
2. The device shall be prepared for use in accordance with the Instructions per User Manual for the device to which the subject is randomized.
3. Proparacaine eye drops will be instilled in both eyes.
4. Therapy will be delivered in accordance with the User Manual for the device to which the subject is randomized.
5. Throughout the treatment visit, subjects will be assessed for any adverse events.

### Safety monitoring

1. Assess and record any adverse events that are observed or reported by the subject
2. Assess and record any treatment device deficiency

